### **Method for handling randomisation, stratification or minimisation factors**

Stratification variables (gender (male/female), schizophrenic status (yes/no), and duration of illness (< 2yrs, ≥ 2yrs)) will be adjusted for in the main analyses.

### **Multiple comparisons and multiplicity**

Comparisons will only be carried out between the two intervention groups. Multiplicity of secondary outcomes will be managed by conservative reporting and interpretation of results. There will be no adjustment of p values.

### **Method for handling time-varying interventions**

CTO is a time varying intervention. The MHA permits a CTO recall to continue for up to 72 hours (i.e. up to 3 nights in hospital) after which the patient either returns to the community on the CTO or the CTO is revoked and the patient remains in hospital under section 3. Recalling patients is therefore a part of the CTO treatment regime which sometimes results in an overnight stay at hospital and thus could be a confounder for the primary outcome. A sensitivity analysis will be carried out adjusting for the number of recalls in the CTO arm.

A secondary sensitivity analysis will be conducted adjusting the primary outcome by the time spent on Section 17 before starting on CTO for those patients with a delayed initiation after allocation.

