## **Outcome measures**

### *Primary outcome*

The primary outcome measure is: psychiatric hospitalisation in the 12-month follow-up period (i.e. from INDEX to 365 days). This is a binary outcome: 1=Patient readmitted at all; 0=Patient never readmitted. A hospitalisation will be defined as the period between the patient's admission date and the date on which the patient leaves

hospital, which should include at least one overnight stay. Hospitalisations can be either voluntary or involuntary.

Recall to hospital of a patient on CTOs will not be classified as readmission (it will be understood as part of the treatment regime). If a recall ends in the CTO being revoked, this will be calculated as a readmission. Any patient who was never initially discharged from hospital after randomisation and remained hospitalised for 365 days after randomisation will be counted as a readmission.

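### Two sensitivity analyses of the primary outcome adjust for post-randomisation variables taken only from the CTO arm, so neither is a sound check on the randomised comparison

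*SAP*

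**What the plan says.** The two analyses stand in SAP section 5, *Method for handling time-varying interventions*.

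- **Recalls.** The rationale first places recall within treatment: "Recalling patients is therefore a part of the CTO treatment regime which sometimes results in an overnight stay at hospital". The same sentence then gives it a second role, saying that it "thus could be a confounder for the primary outcome". The plan that follows is: "A sensitivity analysis will be carried out adjusting for the number of recalls in the CTO arm".
- **Delay.** The second analysis is described as "adjusting the primary outcome by the time spent on Section 17 before starting on CTO for those patients with a delayed initiation after allocation".

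The outcome definition in section 2, *Primary outcome*, bears on both. It covers "psychiatric hospitalisation in the 12-month follow-up period (i.e. from INDEX to 365 days") and is binary. It states "Recall to hospital of a patient on CTOs will not be classified as readmission", but also "If a recall ends in the CTO being revoked, this will be calculated as a readmission". A patient never discharged who "remained hospitalised for 365 days after randomisation will be counted as a readmission".

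The primary model in section 8 is a log-binomial regression for the relative risk of CTO against Section 17. It adjusts for the three baseline stratification factors only. The supporting analyses listed in section 8 consist of the unadjusted model. Neither analysis from section 5 is specified further there. No control-arm value for the covariates, target effect or caution on interpretation is given.

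**The concern.** The rationale is inconsistent. If recall is part of the CTO regime, it lies downstream of allocation and cannot confound a randomised comparison. Conditioning on it breaks the comparability that randomisation gave.

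The outcome definition adds a mechanical link. Revocation follows a recall, and revocation is an event, so some CTO-arm events cannot occur without a recall. Part of the outcome is then on the right-hand side of the model.

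Delay to CTO start is likewise a post-randomisation variable with no Section 17 counterpart. A CTO-allocated patient who is never discharged has no CTO start time, yet counts as an event. The wording also leaves open whether time enters as a covariate or shifts the follow-up window. A shift would give the two arms different windows.

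These are pre-specified analyses of the primary outcome, and section 1.2 commits the team to following the plan as closely as possible. If one of them departs from the primary result, the reader cannot tell real sensitivity from an artefact of the adjustment.

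**Working it through.** The SAP gives no figure for these analyses, so there is none to reproduce. The check asks what the adjusted coefficient becomes when the two treatments are truly equal.

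**Inputs from the SAP:** binary outcome, relative-risk model, 1:1 allocation, two-sided 5% test, recall alone not an event, revocation an event. **Assumed:** 40% readmitted in both arms (p = 0.40), and the recall and revocation shares below. The stratification factors are left out; as baseline variables they do not alter the argument.

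**1. What is compared.** A covariate missing for all Section 17 patients would drop that arm, so it has to be coded zero there. The treatment coefficient is then the contrast at zero recalls: never-recalled CTO patients against all Section 17 patients.

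**2. General formula (adjusting for any recall).** Let f be the share of the CTO arm recalled and q the readmission risk ratio, recalled against not recalled, within that arm. If u is the risk in the never-recalled, then p = (1 − f)u + f·q·u. The adjusted RR is u/p:

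RR = 1/(1 − f + f·q)

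- f = 0.1, q = 2: 1/1.10 = 0.91
- f = 0.2, q = 2: 1/1.20 = 0.83
- f = 0.3, q = 2.5: 1/1.45 = 0.69
- f = 0.3, q = 0.7: 1/0.91 = 1.10

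The truth is 1.00 in every line. The direction turns on whether q is above or below 1.

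**3. Revocation link alone.** Let a share s of CTO readmissions come through revocation, with all other recalls unrelated to risk. The rate of those other recalls cancels, and the risk in the never-recalled is p(1 − s)/(1 − p·s), so

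RR = (1 − s)/(1 − p·s)

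| s | Formula | Simulation |
|---|---|---|
| 10% | 0.90/0.96 = 0.94 | 0.93 |
| 20% | 0.80/0.92 = 0.87 | 0.86 |
| 30% | 0.70/0.88 = 0.80 | 0.80 |
| 40% | 0.60/0.84 = 0.71 | 0.73 |

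At s = 40% and n = 330 (the recruitment target), the simulated test rejects the true null 42% of the time.

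**4. A second scenario, at N = 288.** Assume 50% of readmitted and 20% of non-readmitted CTO patients are recalled. Then f = 0.40×0.50 + 0.60×0.20 = 0.32 and q = (0.20/0.32)/(0.20/0.68) = 2.125. RR = 1/(0.68 + 0.68) = 0.74, against a simulated geometric mean of 0.73. Type I error is 35.5% with the covariate and 4.1% without it.

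**5. Variations under the null.**

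- Recall count as covariate, 25% to 50% of CTO readmissions through revocation: RR 0.64 to 0.87.
- Frailty linking recall and readmission, no revocation link: 0.90 to 0.96.
- Neither link: 1.00.
- Never-discharged patients are events with no recalls, which works against the bias. In one setting RR was 0.93, 0.89 and 0.77 at shares of 10%, 20% and 40%. With 6% never discharged it was 0.96, 0.92 and 0.82, and rejection at the 40% share and n = 330 fell from about 38% to 29%.

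**6. Delay entered as a covariate, under the null.** RR is about 0.89 if longer delay goes with higher risk, 1.14 to 1.16 if it goes with lower risk, and 1.00 if it is unrelated.

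**The case against.** The strongest reply is that these are only sensitivity analyses. The primary model uses baseline factors on the intention-to-treat population, and no decision rule in the SAP depends on either adjustment. That stands, and it limits the seriousness of the point.

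Three stronger readings are tempting, and the document does not support them.

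- **That both analyses build in an apparent CTO benefit.** For recalls this is likely but not certain. Section 5 allows a recall to end in return to the community, which is not an event. If most recalls end that way and avert admission, q falls below 1 and the bias reverses. For delay the direction is undetermined.
- **That recalls are zero by definition in the Section 17 arm.** The *Intent-to-treat population* text lets clinicians change legal status after enrolment and analyses crossovers as randomised. *Derived and computed variables* counts CTO recalls without limiting them to one arm, and *Description of treatments received* lists recalls under both treatments. A Section 17 patient could therefore acquire recalls. The sensitivity analysis as worded takes only those in the CTO arm.
- **That the size is known.** The SAP gives no recall rate, revocation share or control readmission rate. The 42% rejection figure is the upper end of an assumed grid.

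A further objection concerns the obvious alternative of counting overnight recalls as readmissions. It is asymmetric too, because it adds events almost only where recall is part of treatment. With 40% readmitted in both arms and 20% of non-readmitted CTO patients recalled, RR becomes (0.40 + 0.60×0.20)/0.40 = 1.30 if all those recalls are overnight, or 0.46/0.40 = 1.15 if half are. That alternative is usable only as a bound.

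**Conclusion.** The point holds in limited form. With recalls in the model, the coefficient is not the randomised effect. This follows from the SAP's own account of recall and revocation and needs no outside data. The size and direction of the bias do rest on assumptions: about 0.93 to 0.73 in place of 1.00 when 10% to 40% of CTO readmissions come through revocation, small if revocations are few, and possibly above 1 if recalls avert admission. The delay analysis shares the post-randomisation defect and is under-specified, but no direction can be claimed for it. The primary analysis stands. This should be corrected before the analyses are run, but it does not put the main result in doubt.

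**What to change.** 1. Delete both adjusted sensitivity analyses from section 5, and the description of recall as a confounder.
2. If the overnight-stay worry is to be tested, treat it as a question of outcome definition. Rerun the section 8 model on the full intention-to-treat population with any overnight recall, in either arm, counted as a readmission. Label it a bounding analysis that shifts the result against CTO, since recall occurs almost only in that arm and section 2 deliberately excludes it from the outcome.
3. Report recalls by arm, and delay to CTO start for the CTO arm, descriptively only. Section 6 already plans summaries of recall numbers and lengths.
4. If an effect that accounts for recall or delay is wanted, state that target effect and use a causal method with its assumptions declared.

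The cost of items 1 to 3 is SAP wording and one recoded outcome variable from data already collected.

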### **Method for handling outliers**

Ranges will be calculated for all variables and contrasted with a list of possible values for each of them. Any values that resulted too large or too small will be checked by reviewing the relevant patient's booklet. If the value is correct, a sensitivity analysis will be performed excluding it from the analysis to evaluate its effect on the outcomes.

### **Derived and computed variables**

Total scores for the following instruments will be automatically calculated previous to handing the data to the statistician:

- Substance Misuse History (CAGE) –Two scores will be calculated from 2x4 questions: 1) Positive for alcohol (y/n), and 2) Positive for drugs (y/n);
- Leverage - no total score but frequencies of those experiencing each type of leverage;
- MacArthur Admission Experience Survey (AES) –only total scores will be calculated for each of this instrument's subscales: 1) Perceived Coercion Scale; 2) Negative Pressures Scale, and 3) Procedural Justice Scale;

- Index of fairness;
- Index of effectiveness;
- Insight and Treatment Attitudes Questionnaire (ITAQ);
- Scale to Assess Therapeutic Relationship in Community Mental Health Care – Participants version (STAR –P) total score –and three subscale scores: 1) Positive Collaborations, 2) Positive Clinician Input, and 3) Non Supportive Clinician Input;
- Autonomy Preference Index (API) – only total scores will be calculated for the two subscales 1) Decision-making scale, and 2) Information Seeking Scale;
- Client Satisfaction Questionnaire (CSQ-8);
- Health Related Quality of Life Questionnaire (EQ-5D);
- Drug Attitude Inventory (DAI);
- Brief Psychiatric Rating Scale (BPRS);
- Global Assessment of Functioning (GAF).

Contact with service will be obtained by summing up questions 1-6 and 10 from the Client Service Receipt Inventory section of the CRF. The total number of contacts with carers of any profession will be calculated as well as the total number of phone and face-to-face contacts.

The following variables will be manually calculated previous to locking the dataset by comparing admission and discharge dates from (a) Index to 180 days; (b) 181 days to 365 days; (c) Index to 365 days:

- Number of nights to readmission;
- Total number of days in hospital;
- Total number of involuntary readmissions. A readmission will be considered involuntary if there is at least one change of status to “involuntary” between the admission and discharge dates;
- Total number of voluntary readmissions;
- Total number of CTO recalls.

## **Planned sub-groups**

Sub-group analysis will be performed only for primary outcome and all secondary outcomes apart from time under compulsion. The subgroups to be tested are as follows:

- Age:  $\leq 40$  years vs.  $> 40$  years;
- Gender: male vs. female;
- Ethnicity: white vs. black vs. Asian vs. other; and black vs. other;
- Born in UK: born in UK vs. born in another country;
- Marital status: (single+separated/divorced) vs. married/co-habiting;
- Accommodation: independent vs. (supported + homeless);
- Living status: living alone (living alone +homeless + living in supported housing) vs. living with others (living with partners/family+ with others e.g. friends);
- Diagnosis: schizophrenia vs. other;
- Duration of illness:  $<2$  years vs.  $\geq 2$  years;
- Educational level:  $\leq 12$  years vs.  $> 12$  years; Tertiary education y/n;
- Type of service: Assertive Outreach and Forensic vs. CMHT vs. Learning Disability vs. Crisis Intervention teams vs. Rehabilitations vs. EIS vs. Other;
- Scales:
  - BPRS:  $\leq 33$  vs.  $> 33$ ;
  - GAF:  $\leq 49$  vs.  $> 49$ .

## **6. Descriptive analysis**

### **Participant flow**

Participant flow will be summarized in a CONSORT diagram.

### **Description of treatments received**

For CTOs, the number of recalls and their lengths will be summarized. For both treatments, the time to initial discharge after randomisation and subsequent occurrences will be summarized according to:

- Number of hospitalisations;

- Average length of hospital stays;
- Changes to legal status;
- Total number of tribunals (MHRT);
- Total number of Managers Hearings;
- Number of recalls and revocations;
- Discharges;
- Average duration on CTO and on Section 17 Leave;
- Number of people who never leave hospital during the trial period;
- Number of patients whose voluntary hospitalisation is made involuntary during admission;
- Average number of service contacts received;
- Time under legal compulsion (including recalls);
- Number of
  - Face-to-face contacts with service;
  - Phone contacts with service.

### **Baseline comparability of randomised groups**

The baseline comparability of the two randomised groups will be assessed by tabulating patient characteristics and treatment experiences. No statistical tests on baseline data will be performed.

For continuous variables, normality will be assessed using plots. For normally distributed continuous variables, mean and standard deviation will be reported. For non-normally distributed continuous variables, median and interquartile range will be reported in addition to the mean. For binary and categorical variables, number of cases and percentages over non-missing observations per category will be reported. However, some data will be presented based on the format that will convey most information which may involve collapsing some variable with large numbers of possible categories (such as self-reported ethnicity) into a smaller list of categories (e.g. white/black/Asian/mixed/other). Collapsed categories will be identified (such as in a footnote to the table) so that it is known what is included in each category. Similarly although age and other variables are measured on a continuous scale, it may be more informative to present the percentages at different age intervals.

Summary of all baseline characteristics will be presented by treatment group and overall.

Tables will include:

- Socio-demographic characteristics;
- Employment, family and living situation;
- Clinical and medical history;
- Substance Misuse History (CAGE for alcohol and CAGE for drugs);
- Legal history;
- Leverage;
- AES (Perceived Coercion, Negative Pressures, and Procedural Justice);
- Index of fairness;
- Index of effectiveness;
- Types of pressure;
- Psychiatric Autonomy Preference Index (API);
- Insight and Treatment Attitudes (ITAQ);
- Therapeutic relationships (STAR-P);
- Client Satisfaction Questionnaire (CSQ-8);
- Global Assessment of Functioning (GAF);
- European Quality of Life Questionnaire - 5 Dimensions (EQ-5D);
- Brief Psychiatric Rating Scale (BPRS-24);
- Drug Attitude Inventory (DAI).

### **Current psychiatric medication**

Current medication will be summarized at each time point by treatment group, tabulating the number of psychiatric medications per person; the generic name of the medication, and average daily dose (mg).

### **Characteristics of care providers where applicable**

Baseline number of care providers (1. Assertive Outreach and Forensic, 2. CMHT, 3. Learning Disability, 4. Crisis Intervention teams, 5. Rehabilitations, 6. EIS, 7. Other)

will be tabulated by treatment group and full sample as well as number of patients under each care type.

### **Comparison of losses to follow-up**

As the main outcomes relate to hospital admissions data obtained from medical records, it is not expected that there will be any missing data for these outcomes. Participant self-reported outcomes derived from interviews and questionnaires are expected to contain substantial missing data.

The baseline characteristics of patients with and without data will be tabulated by treatment group and overall at each follow-up point for participant self-reported outcomes.

### **Tabulation of protocol violations**

Protocol violations will be tabulated by treatment group and overall.

## ***7. Interim analysis and safety monitoring analyses***

### **Purpose of interim analyses**

Two interim analyses were reviewed by the Data Monitoring Committee (DMC), which forms part of OCTET's governance structure. The purpose of the interim analyses was to judge whether it was ethical and desirable to continue the trial by examining interim data.

### **Monitoring plan**

The first interim analysis was carried out in May 2010; the second, in February 2011. Each of these interim analyses reported:

- Overall progress;
- Participant accrual;
- Data quality, availability and completeness;
- Baseline data;
- Comparison of primary and secondary outcomes (including EQ-5D and GAF).

## **Stopping rules**

The DMC was asked on the basis of the interim results to assess whether the trial should be stopped because:

- There are unanticipated adverse outcomes clustered in one arm;
- The result already is clear (i.e., statistically clear advantage to one arm because of massive effect size).

The stopping rules were not statistically defined a-priori and thus there will be no adjustment of p-values in the main analysis as this would constitute a post-hoc decision.

In both interim analyses the DMC unanimously recommended the continuation of the trial.

## **8. *Analysis of primary outcome***

### **Descriptive statistics for outcome measure**

Number of patients readmitted to hospital in the 12-month follow-up; the proportion these patients represent and a 95% confidence interval for this proportion, by treatment group and overall.

### **Primary analysis**

The primary outcome, psychiatric hospitalisation in the 12 month follow-up period, will be analysed using log-binomial regression adjusted for stratification factors (gender (male/female), schizophrenic status (yes/no), and duration of illness (< 2yrs,  $\geq$  2yrs)). Results will be presented as the relative risk of readmission under CTO compared to Section 17, with appropriate 95% confidence interval and 2-sided p-values.

If log-binomial modelling is not possible due to model instability then other alternatives will be explored such as Poisson regression with robust error variances, a method which has the advantage of presenting results as relative risks; or logistic regression with associated odds ratios.

The primary analysis will be conducted on the ITT population. There will be no adjustment for missing data as it is not expected that there will be any.

### **Other analysis supporting the primary (including sensitivity analyses)**

A sensitivity analysis will be conducted for the primary outcome which is unadjusted for any stratification factors.

## ***9. Analysis of secondary outcomes***

### **Descriptive statistics for outcome measures**

For all secondary outcomes, we will report the number and percentage of observed values, mean and standard deviation, median and inter-quartile range, and range, by arm and full sample.

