### *Secondary outcomes*

Secondary outcomes related to readmission follow the same readmission definition and constraints stated for the primary outcome. Secondary outcomes considered in this study are mainly obtained from medical records. They represent patterns of readmission and are listed next.

**Number of nights in psychiatric hospitalization from INDEX to 365 days.** This will include voluntary and involuntary hospitalizations. Nights on recall will not be included.

**Number of nights to first readmission from INDEX to 365 days.** Time to first readmission for patients (in both arms) that remained in hospital for the duration of the trial will be counted as zero. Nights on recall do not count as a readmission.

**Number of readmissions from INDEX to 365 days.** This will include voluntary and involuntary hospitalisations but not nights on recalls.

**Time under legal compulsion.** This will be measured by time being subject to the Mental Health Act (i.e. under sections 2, 3, 17, 37 or on a CTO).

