### **Secondary analysis**

Secondary analyses will be conducted using the ITT population. No adjustment for missing data will be performed when analysing these outcomes as no missing data is expected for them.

Secondary outcomes will be analysed in the same way as primary outcomes using multiple regression models with adjustment for stratification factors. The type of regression model will depend on the data distribution. All model assumptions will be assessed.

Number of readmissions and number of nights in psychiatric hospitalization are count outcomes and will be analysed using Poisson or negative-binomial regression models depending on data dispersion. Results will be presented as incident-density ratios, which are interpreted in the same way as relative risks.

The number of nights to first readmission from INDEX to 365 days, and time under compulsion, are time to event outcomes and analyses will be performed using proportional hazards regression, with results presented as hazard ratios with 95% confidence intervals. Kaplan Meier plots will also be presented and the median time to readmission calculated with 95% confidence intervals.

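### Minor: nights to first readmission is to be described by mean, SD, median, IQR and range like a fully observed variable, with no value or censoring rule for patients discharged and never readmitted

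*SAP*

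**What the plan says.** The opening of SAP Section 9 (Descriptive statistics for outcome measures) sets a single rule, by arm and for the full sample: "For all secondary outcomes, we will report the number and percentage of observed values, mean and standard deviation, median and inter-quartile range, and range". No outcome is exempted.

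The list of secondary outcomes in Section 2 includes "Number of nights to first readmission from INDEX to 365 days". It gives one rule for a patient without a readmission date: "Time to first readmission for patients (in both arms) that remained in hospital for the duration of the trial will be counted as zero". The primary outcome foresees patients who are not readmitted, since its coding is "1=Patient readmitted at all; 0=Patient never readmitted". Nothing says what such a patient, once discharged, contributes to the nights variable.

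Section 5 (Derived and computed variables) says how the variable is built: "The following variables will be manually calculated previous to locking the dataset by comparing admission and discharge dates", over the two half-years and the whole year.

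Section 9 (Secondary analysis) says that nights to first readmission and time under compulsion "are time to event outcomes and analyses will be performed using proportional hazards regression". It adds: "Kaplan Meier plots will also be presented and the median time to readmission calculated with 95% confidence intervals". Of the secondary outcomes in general it says that "no missing data is expected for them".

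**The concern.** Section 9 handles one variable in two ways. The descriptive rule treats it as a number that every patient has. The regression treats it as a time that is censored for some patients. The SAP does not connect the two, because the discharged, never-readmitted patient has no stated value and no stated censoring time.

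If the variable is simply the interval to a recorded admission date, these patients are blank. The by-arm mean, SD, median, IQR and range then describe only readmitted patients. Whether a patient belongs to that subset is itself the trial's outcome, so the comparison is no longer between randomised groups. A treatment that prevents readmissions removes patients from the summary instead of lengthening their times. A reader of the table could see a much smaller effect than the trial found, or, for some patterns of effect, one in the wrong direction.

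**Working it through.** **1. The plan's own figure, to find plausible rates.** Section 3 (Sample size determination) gives 288 patients, a 16-point difference, 5% significance and 80% power. It states no control rate, so 288 cannot be rebuilt from the SAP alone. The pooled-variance formula, two-sided and 1:1, is

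n per arm = [1.96·√(2p̄(1−p̄)) + 0.8416·√(p₁(1−p₁)+p₂(1−p₂))]² / 0.16².

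For 46% v 30% this gives [1.345 + 0.570]²/0.0256 = 143.3, so 144 per arm and 288 in total. The mirror pair 70% v 54% gives the same total. The pairs 48% v 32% and 68% v 52% each give 292. I use 48% v 32% as the main illustration. It is an assumption.

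**2. Constant hazard, complete follow-up, no never-discharged patients (assumptions).** For a proportion p readmitted by day 365:

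- hazard h = −ln(1−p)/365
- restricted mean R = p/h
- mean among the readmitted M = (R − 365(1−p))/p

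Section 17, p = 0.48: h = 0.0017916, R = 267.9, M = (267.9 − 189.8)/0.48 = 163.

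CTO, p = 0.32: h = 0.0010566, R = 302.9, M = (302.9 − 248.2)/0.32 = 171.

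The same formulas over a range of control rates, always with a 16-point difference:

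| Readmitted, Section 17 v CTO | Mean among readmitted (gap) | Restricted mean (gap) |
|---|---|---|
| 36% v 20% | 169 v 176 (7) | 294 v 327 (33) |
| 48% v 32% | 163 v 171 (8) | 268 v 303 (35) |
| 60% v 44% | 155 v 165 (10) | 239 v 277 (38) |
| 68% v 52% | 149 v 160 (12) | 218 v 259 (41) |

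The readmitted-only gap is about a fifth to under a third of the restricted-mean gap. At 48% v 32% with 144 per arm, the readmitted-only mean was lower under CTO in 34% of 20,000 simulated trials.

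**3. An effect that is only late (assumption).** Keep 48% v 32%, but let 24% of each arm be readmitted at day 90, with a further 24% v 8% at day 273.

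- Among the readmitted: (0.24·90 + 0.24·273)/0.48 = 181.5 v (0.24·90 + 0.08·273)/0.32 = 135.8. CTO looks 46 nights worse.
- Restricted mean: 21.6 + 65.5 + 0.52·365 = 276.9 v 21.6 + 21.8 + 0.68·365 = 291.6. CTO is 15 nights better.

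A milder version has equal hazards to day 60 and a reduced CTO hazard afterwards. It also reverses: about 163 v 150 among the readmitted, against restricted means of 268 v 296.

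**4. The other reading: 365 entered for the never-readmitted.** The plain mean then equals the restricted mean (268 v 303). The descriptive median, however, is 365 in both arms whenever fewer than half of each are readmitted, so it shows no difference.

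**5. The Kaplan-Meier median.** With 144 per arm and no earlier censoring, it is reached if at least 72 patients are readmitted. The binomial chance is about 0 at 32% readmitted, 9% at 44%, 35% at 48%, 71% at 52% and 99% at 60%. At the lower pair of rates it is expected in neither arm. At the mirror pair it is expected in both.

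**The case against.** The strongest reply is that the SAP nowhere restricts the mean or median to readmitted patients. In the descriptive rule, the reference to observed values belongs to the count and percentage and serves as a completeness check. The same section expects no missing data for the secondary outcomes, which is hard to square with a variable left blank for everyone not readmitted. The variable is also bounded at 365 days. If those patients carry 365, the plain mean is the restricted mean and nothing is reversed. This stands in part. The readmitted-only reading is an inference from how the variable is derived, not something the SAP states. But the SAP does not state the other reading either, and under it the generic median can still be uninformative.

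The second reply also stands. Censoring is handled where it matters: in the proportional hazards model, in the Kaplan-Meier plots, and in the Section 8 proportions readmitted with confidence intervals. With complete follow-up, those proportions already give the complement of the Kaplan-Meier figure at day 365.

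Third, a reader might infer that the planned Kaplan-Meier median is a defect because it may not be estimable. The documents do not support that. A median that is not reached is a valid result, and whether it happens depends on readmission rates that the SAP does not state.

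Fourth, the reversal needs an effect confined to later readmissions, which nothing in the SAP predicts. Under constant hazards the expected direction stays right.

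**Conclusion.** The point holds as a minor one. A stated descriptive rule does not suit a censored outcome, and the SAP gives no value or censoring convention for discharged, never-readmitted patients. On the most natural reading, the by-arm table would compare subsets selected by the outcome. Under the assumed 48% v 32% and constant hazards, a 35-night difference would appear as 8. The rates, the hazard shape and the late-effect patterns are all illustrations.

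A reader might go further and conclude that the plan will misstate the CTO effect, or that it offers no usable summary of this outcome. Neither follows. The defect is confined to one row of a descriptive table. The hazard ratio, the Kaplan-Meier plots, the primary analysis and the sample size are not touched.

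**What to change.** In Section 9, exempt nights to first readmission from the generic descriptive rule. State that patients discharged and never readmitted are censored at day 365. For this outcome report, by arm:

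- the number of events and the number censored;
- the Kaplan-Meier proportion free of readmission at 180 and 365 days, which match the windows in Section 5;
- the restricted mean nights to day 365, with the between-arm difference and its 95% confidence interval.

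Keep the planned Kaplan-Meier median, and say that it is reported as not reached where fewer than half of an arm are readmitted.

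The cost is a few sentences and no new data. The change is best made before database lock, because Section 5 derives the variable before then.
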